7.4.1 Changes in Analysis in Comparison to Study Protocol

The analyses described in this analysis plan are consistent with the analyses described in the study protocol.

7.4.2 Study Data

Study data identified in the schedule for time and events (Table 4-1) are collected, and source verified, on the electronic data capture (EDC) product Medrio. HAAH tissue, HAAH serum, PBMC, and immunological blood testing results are not collected in the EDC tool and are provided by Sensei Biotherapeutics.

All study data will be formulated into regulatory compliant data sets to provide transparency, traceability, and integrity of trial analysis results from the collection source. Observed study data will be mapped to the CDISC Study Data Tabulation Model (SDTM) and serve as the source data from the trial. All study analyses will be completed using analysis data sets that are derived from the SDTM and follow the CDISC Analysis Data Model (ADaM) architecture. All planned analyses will be performed using the ADaM data sets developed for this study.

7.4.3 Coding

Coding of AEs will be performed on an ongoing basis throughout the study by Accelovance Safety. Verbatim terms that are entered into the database by the site will be coded manually; if necessary a query will be created to obtain clarification from the site. These events will be mapped to the MedDRA (Version 18.1) system for reporting (preferred term [PT] and system organ class [SOC]).

Concomitant medications will be coded using World Health Organization (WHO) Drug Dictionary (B Format – June 2015). Medical history data will not be coded.

7.4.4 Statistical Software

Data manipulation, tabulation of descriptive statistics, calculation of inferential statistics, and graphical representations will be performed primarily using SAS (release 9.2 or higher) for Windows. If the use of other software is warranted, the final clinical study report will detail what software was used and for what purposes.

7.4.5 Derived Variables

- Non Treatment Emergent Adverse Events include all AEs that stopped the day prior to the first vaccination, started prior to the first vaccination but did not increase in severity or relationship during treatment, or started more than 30 days after *the final study treatment administration* date.
- Treatment Emergent Adverse Events (TEAEs) include all AEs that start on or after the first study treatment administration, or AEs that are present prior to the first administration, but their severity or relationship increases after the first administration up to and including 30 days after the final administration date.
- Change from baseline will be calculated as the observed value at the current visit or time point minus the observed value at baseline.
- Number of doses administered will be calculated for each subject by summing the number of doses administered over all visits.
- *Prior medications* include all medications that have a start date prior to the date of first study treatment administration.
- Concomitant medications include all medications that are taken on or after the date of first study treatment administration.
- The end of treatment phase visit will be the visit immediately after the last visit where treatment was administered. This visit will be the first follow up visit for subjects who have any follow up visits, or the End of Study visit for all other subjects.

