sample will not be entered into the treatment phase as they are not deemed suitable candidates for the HAAH vaccine. The 21-day treatment phase will allow the patient sufficient time to recover from any adverse effects of the vaccine before the next dose. It is anticipated that the SNS-301 will lead to the development of active anti-HAAH immunity with consistent polyclonal anti-HAAH antibody titers in addition to development of anti-HAAH T-cells. This is further supported by our current data from patients treated up to now. Based on this, a decision has been made to limit the total number of injections to 9, which accounts for 6 months of treatment with an additional 6 months of follow up, with monthly measurement of PSA levels and anti-HAAH immunity parameters. Patients who, at the time of this amendment, have received more than 9 injections, will cease treatment at the time of their last injection when this amendment goes into effect and will also be followed for 6 months, as will patients whose disease progression leads to treatment stoppage before 1 year. Patients with evidence of progression and declining HAAH immune parameters have the option of resuming therapy on the study protocol in the 6 month follow up period. All patients are eligible for enrollment in the expanded access protocol after study closure.

4. Study Objectives and Endpoints

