5.2.4 Enrollment Holds

Enrollment will be held if the subject experiences a grade 3 or greater ASR as determined by the Investigator. The subject must be withdrawn from the study if they experience a grade 3 ASR. Enrollment can be re-started after agreement between the Principal Investigator, Medical Monitor, and the Sponsor.

Study enrollment will be halted in the event of a death of a subject while on the study or within a 30-day period follow study drug exposure regardless of drug relationship. In the event the enrollment is halted, a clinical review of the subject case will be made by the Principal Investigator, Medical Monitor, and the Sponsor to assess the safety of the medicinal product. If the review concludes there is no association of the death with the study drug, restarting enrollment may proceed.

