5.5.2.6 Additional treatment: Every additional 21 days ± 3 days if indicated

A maximum of 9 drug administrations will be administered on this study for all patients, except in the case of progression on study and or in the case of patients who had been on study for more than 6 months at the time of this amendment. Patients with evidence of progression and declining HAAH immune parameters within 6 months of stopping therapy have the option of resuming therapy on the study protocol.

- Immunologic blood collection pre-dose on day of drug administration every 21 days thereafter if continuing treatment.
- Symptom-directed physical examination
- Vital signs and ECG
- Eastern Cooperative Oncology Group (ECOG) performance score
- Prostate-specific antigen (PSA) assessment
- Biochemical testing: chemistry, hematology, coagulation, CH50
- Study treatment administration
- Physician administration site assessment (post-administration)
- Adverse events and concomitant medications

5.5.2.7 Follow up and End of Study (EOS): 28 days \pm 3 days after last treatment for a total of 6 months

- Complete physical examination
- Vital signs
- Eastern Cooperative Oncology Group (ECOG) performance score
- ECG
- Prostate-specific antigen (PSA) assessment
- Clinical laboratory tests, chemistry, hematology, coagulation, CH50 (only on first follow up)
- Immunologic blood collection
- Adverse events and concomitant medications

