5.5.3.5 Adverse Events (AE)

Adverse event means any untoward medical occurrence associated with the use of a drug in humans, whether or not considered drug related and occurs after the patient is given the first dose of study drug. Any AE that occurs prior to the first dose is part of the medical history.

At least 30 minutes post dose, the Investigator should evaluate the site of drug administration and query the patient in a general manner regarding the presence of any untoward effects.

Laboratory abnormalities (grade 1 and greater that are listed in the NCI-CTCAE V4.03) should be recorded on the AE page regardless of their causality. Worsening of a pre-existing condition is also considered an AE as is the discovery of an abnormal finding during physical exam that was not included in the medical history.

Patients will be encouraged to spontaneously report any AE. Study personnel will ask open-ended questions to obtain information about AEs at every visit. Date and time of onset and resolution (if applicable) of the AE will be documented.

Causality

Events will be considered treatment related if classified by the Investigator as possible, probable, or definitely associated with the use of the drug. Association of events to the study treatment will be made using the following definitions:

| Term | Definition |
|----------------|--|
| Definitely Not | The event is definitely not associated with study treatment. |
| Probably Not | The temporal association, patient history, or clinical condition is such that the study treatment is not likely to have had an association with the observed event. |
| Possible | The event: a) follows a reasonable temporal association with the study treatment administration, but b) could have been produced by the patient's clinical condition or other therapy. |
| Probable | The event: a) follows a reasonable temporal association with the study treatment, b) abates upon discontinuation of study treatment, and c) cannot be reasonably explained by the patient's clinical condition or other therapy. |
| Definite | The event: a) follows a reasonable temporal association with the study treatment, b) abates upon discontinuation of study treatment, c) cannot be reasonably explained by the patient's clinical condition or other therapy, and d) reappears on re-exposure to the study treatment. |

Severity

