5.5.3.6 Serious Adverse Event (SAE)

A serious adverse event (SAE) is an AE that:

- Is fatal
- Is life-threatening, meaning the patient was, in the view of the Investigator, at immediate risk of death from the reaction as it occurred, i.e., it does not include a reaction that, had it occurred in a more serious form or progressed, might have caused death
- Is a persistent or significant disability or incapacity or substantial disruption of the ability to conduct normal life functions
- Requires or prolongs inpatient hospitalization
- Is a congenital anomaly or birth defect

Other important medical events may be considered SAEs when, based upon appropriate medical judgment, they may jeopardize the patient and may require medical or surgical intervention to prevent one of the outcomes as listed (# 1-5 above) in this definition.

All SAEs, including death due to any cause, that occur during this study and until 30 days after the last dose of study treatment, whether or not expected and regardless of causality, must be reported to the Medical Monitor immediately upon discovery of the event, using an SAE Form.

The Medical Monitor will advise the Investigator regarding the nature of any further information or documentation that is required. The Investigator should provide the following documentation at the time of notification if available:

- SAE Form
- AE (CRF) page
- Concomitant and support medication pages
- Relevant diagnostic reports
- Relevant laboratory reports
- Admission notes
- Hospital discharge summary (when available).

The Sponsor must notify FDA and all participating Investigators (i.e., all Investigators to whom the Sponsor is providing drug under its INDs or under any Investigator's IND) in an IND safety report of potential serious risks, from clinical trials or any other source, as soon as possible, but in no case later than 15 calendar days after the Sponsor determines that the information qualifies for reporting under paragraph (c)(1)(i), (c)(1)(ii), (c)(1)(ii), or (c)(1)(iv) of 21CFR 312.32. The Sponsor must identify all IND safety reports previously submitted to

FDA concerning a similar suspected adverse reaction, and must analyze the significance of the suspected adverse reaction in light of previous, similar reports or any other relevant information.

Serious and unexpected suspected adverse reaction

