8.6.2 Adverse Events

The number and percent of subjects with any TEAEs will be displayed by SOC and PT for each dosage group. For additional treatment visits and end of study, the level used as the dosage group will be determined by the dose level the subject took at the start of the TEAE. Within each PT, subjects will be counted only once if they had more than one event reported during the treatment period.

For MedDRA SOC, the number and percentage of subjects experiencing at least one TEAE overall and at least one TEAE for a system will be tabulated by severity grade (Grades 1-5) and dosage group. For MedDRA PT, the number and percentage of subjects reporting at least one TEAE within a PT category will be tabulated by relationship to study products and dosage group. For the calculations in these tables, each subject's TEAEs will be counted once under the maximum severity or the strongest recorded causal relationship to study product.

Summaries will be generated for all serious TEAEs and all TEAEs causing permanent dose discontinuation by SOC and PT for each dosage group.

A listing will be produced for all subjects who reported serious TEAEs. The listing will provide details of the events including severity, relationship to study product, time between onset and last study treatment administration, and a summary of the event.

All TEAEs and non-treatment emergent AEs will be listed individually by subject.

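### SAP 7.4.5 gives two overlapping rules for AEs starting more than 30 days after the last dose; on the likelier reading, late related or serious events drop out of the TEAE tables and the serious-event listing

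*SAP*

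**What the plan says.** **Collection.** Protocol Table 1 and section 5.5.2.7 schedule follow-up visits every 28 ± 3 days, "after last treatment for a total of 6 months", and the assessments there include "Adverse events and concomitant medications". Protocol 5.5.3.5 defines an AE as something that "occurs after the patient is given the first dose of study drug"; it sets no end date and no onset limit on the Investigator's causality rating. Protocol 3.4 describes nine injections "with an additional 6 months of follow up, with monthly measurement of PSA levels and anti-HAAH immunity parameters".

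**Classification.** In SAP 7.4.5, one bullet makes an event non treatment emergent if it preceded dosing but "did not increase in severity or relationship during treatment, or started more than 30 days after" the final administration date. The next bullet defines TEAEs in two limbs: new events starting on or after the first dose, and pre-existing events that worsen. As punctuated, the 30-day limit attaches only to the second limb.

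**Display.** SAP 7.4 puts assessments from the 6-month follow-up in listings only, unless noted otherwise. SAP 8.6.2 tabulates TEAEs by SOC and PT, severity, relationship, seriousness and dose discontinuation. For serious events it adds: "A listing will be produced for all subjects who reported serious TEAEs". It lists all TEAEs and non-TEAEs by subject.

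**Serious events and deaths.** Protocol 5.5.3.6 requires immediate notification of SAEs "that occur during this study and until 30 days after the last dose of study treatment". Protocol 5.2.4 says: "Study enrollment will be halted in the event of a death of a subject while on the study", and goes on to add a 30-day period following drug exposure.

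**The concern.** Overall safety is a stated secondary objective in both documents. Protocol 3.1 describes the target as a self-antigen whose tolerance the vaccine must overcome, so a delayed immune-mediated event is a plausible harm, and the long follow-up is where it would be seen. With about 18 patients, a single related event is 1/18 = 5.6% overall, or 1/6 = 17% in a cohort of six. Whether it enters the incidence tables therefore changes the reported result.

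The SAP carries other follow-up data into summaries. Section 8.5 runs PSA velocity and doubling time to end of study (Table 14.2.3.2.3), and section 8.4 describes concomitant medications at follow-up visits. Adverse events get no comparably clear provision. Two programmers following 7.4.5 could also classify the same event differently.

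**Working it through.** The plan states no figure on this point to reproduce. The check compares the collection and reporting windows, then traces one event through the rules.

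**1. Follow-up days outside the 30-day window**

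Collection: six 28-day intervals (Table 1, 5.5.2.7), 6 × 28 = 168 days. If 6 months is read as calendar time, 182 or 183 days (assumption). Reporting window: 30 days after the final administration (SAP 7.4.5).

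Share outside = (T − 30) / T:
- T = 168: 138/168 = 82%
- T = 182: 152/182 = 84%
- T = 183: 153/183 = 84%

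Nominal visits fall on days 28, 56, 84, 112, 140 and 168. With ± 3 days, the first spans days 25 to 31 and the second starts at day 53, so five of six visits fall wholly after day 30.

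**2. Share of all AE-observed time**

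For n doses on schedule, share = (T − 30) / [(n − 1) × 21 + T].
- n = 9, T = 168: 138/(168 + 168) = 138/336 = 41%
- n = 9, T = 182: 152/(168 + 182) = 152/350 = 43%

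This share depends on n. Illustrations with T = 168: three doses give 138/(42 + 168) = 66%; twelve doses give 138/(231 + 168) = 35%.

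**3. One event through SAP 7.4.5**

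Take a new AE starting 45 days after the final dose, judged probably related and serious.
- Non-TEAE bullet: 45 > 30, so it is non treatment emergent.
- TEAE bullet, first limb: it starts after the first dose, so it is treatment emergent.

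Both rules apply and no precedence is stated.

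**4. Which reading is likelier**

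For exclusion:
- The non-TEAE bullet names late onset explicitly.
- SAP 7.4 keeps follow-up assessments out of tables by default.
- SAP 8.6 carries safety summaries only to the end of treatment phase visit, which 7.4.5 defines as the first follow-up visit where there is one.
- In SAP 10.1 the AE tables are titled either through Day 43 or for additional treatment visits; none is titled for follow-up.

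Against: SAP 8.6.2 gives a dose-grouping rule for TEAEs at additional treatment visits and end of study, which suggests that some TEAEs may be expected that late.

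**5. Where the event appears if excluded**

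| Display | Can it hold the day-45 event? |
|---|---|
| 14.3.2.1 (overall AE summary) | Unknown: title not restricted to TEAEs, shells in a separate document |
| 14.3.2.2 to 14.3.2.6 | No: TEAEs only |
| 14.3.2.7 (serious events) | No: serious TEAEs only |
| 16.2.7 (by-subject AE listing) | Yes |

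**6. Resumed dosing**

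The 30 days run from the final administration. If a patient resumes SNS-301 during follow-up, events in the off-treatment gap precede the final dose and count as TEAEs. The exclusion applies only after the last dose ever given.

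**The case against.** The strongest reply is that the SAP openly chooses listings for follow-up data. Nothing collected is hidden: all non-TEAEs are listed by subject. With about 18 patients and no formal analysis under Protocol 6.1, a listing can be read in full. A 30-day TEAE window can reasonably stand for the main tables, and the TEAE bullet, taken literally, may not exclude new late events at all.

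Much of this stands. The data are not lost, and the main tables need not change their window. But a line listing gives no incidence by term, grade or relationship, and the detailed serious-event listing would omit a late SAE. The literal TEAE reading does not rescue the plan either, because it leaves two definitions that contradict each other.

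A reader might go further in three ways that the documents do not support:
- **That late related or serious events certainly reach no safety table.** The definitions conflict, 8.6.2 mentions end of study, and the content of Table 14.3.2.1 cannot be seen.
- **That Protocol 5.2.4 and 5.5.3.6 contradict each other.** Both combine study participation with a 30-day period, and they serve different purposes (an enrollment halt and SAE notification). The wording in 5.5.3.6 is ambiguous, since participation includes the 6-month follow-up. That is a lack of clarity, not an established contradiction.
- **That about 82% of late harm would be missed.** The figure is calendar time; the documents give no late-event rate.

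**Conclusion.** The point holds as an unresolved overlap in SAP 7.4.5 with a probable reporting gap. The overlap is certain from the text. The gap depends on the exclusion reading, which the surrounding rules favor but do not settle. On that reading, AEs starting in 82% to 84% of the post-treatment period are left out of the TEAE tables and the serious-event listing even when judged related or serious. The percentage assumes a patient who completes follow-up and does not resume dosing. The 41% to 43% share of total observed time further assumes exactly nine doses on schedule; it is larger with fewer doses and smaller with more.

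This should be corrected before the tables are produced, because it determines the reported incidence of related and serious events for a stated objective. It does not affect the MTD, which rests on the first 21 days.

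**What to change.** 1. **SAP 7.4.5:** rewrite the TEAE and non-TEAE definitions to be mutually exclusive, with the 30-day limit applied to both limbs of the TEAE definition.
2. **SAP 7.4 and 8.6.2:** keep the 30-day TEAE tables. State an exception to the follow-up rule and add one summary of AEs starting more than 30 days after the final dose, to end of study. Show SOC and PT, grade, relationship and seriousness, with last dose level and time since last dose.
3. **Listing 14.3.2.7:** extend it to all SAEs, flagging those that are not treatment emergent.
4. **Table 14.3.2.1:** state which events it counts.
5. **Protocol 5.5.3.6:** clarify what the SAE notification period means for the 6-month follow-up, and reconcile it with 5.2.4 and the AE collection schedule. The documents do not say whether an SAE form is required for an event found at a visit after day 30, and the completeness of the wider listing depends on that.

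Items 1 to 4 cost SAP wording, one table and a wider listing, using AE data already scheduled for collection. Item 5 is a protocol clarification. The small downside is that more background disease events will be displayed; the relationship column separates them.

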7.4.6 Data Handling

Any administration site reaction found in the AE log that is also captured on the Physician Administration Site Assessment eCRF page will not be counted as an (unsolicited) AE to avoid duplication.

Unscheduled or repeated laboratory results will not be analyzed for the summary of continuous values.

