7.4 Analysis of the Study

All statistical tests will be two-sided and a difference resulting in a p-value of less than or equal to 0.05 will be considered statistically significant. All p-values will be rounded to and displayed in four decimals. If a p-value less than 0.0001 occurs it will be shown in tables as <0.0001.

There will be no multiplicity adjustments.

Descriptive summaries of variables will be provided where appropriate. For continuous variables, the number of non-missing values (n) and the median, mean, standard deviation, minimum, and maximum will be tabulated by dosage group. For categorical variables, the counts and proportions of each value will be tabulated by dosage group. Since this study allows for subjects to change their dose level during additional treatment visits after Day 43, the dose level can change over the course of the study; see Section 8 for how summaries by dosage group will be handled when dose levels vary.

Expansion of descriptive table categories within each treatment may occur if such elaborations are thought to be useful.

Assessments completed during the 6-month follow up period after study treatment will not appear in any tables or graphs (unless noted otherwise), but will be included in the data listings, classified under the last dose level the subject took at the last treatment visit prior to the end of study.

All collected data will be presented in listings. Data not subject to analysis according to this plan will not appear in any tables or graphs but will be included in the data listings.

Post-hoc exploratory analyses not identified in this SAP may be performed to further examine the study data. These analyses will be clearly identified as such in the final clinical study report.

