8.6.1 Administration Site Reactions

Administration Site reactions include local (injection site) reactions, such as pain, tenderness, erythema/redness, and swelling. Events are collected via the Physician Administration Site Assessment eCRF page and are graded using a severity rating of 0 (none), and 1, 2, 3, 4 (mild, moderate, severe, potentially life threatening).

A summary of the number and percentage of subjects experiencing at least one administration site reaction anytime after the first study treatment administration will be tabulated by reaction type, maximum severity, and dosage group through Day 43, and separately, for additional treatment visits after Day 43. A separate summary will be tabulated for each visit that an assessment is scheduled.

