10.1 List of Tables, Figures, and Listings

Table No.	Description of Table	Population
4.1.1	Subject Disposition	All Subjects
4.1.2.1	Demographics and Baseline Characteristics	Safety
14.1.2.2	Demographics and Baseline Characteristics	Immunologic
14.2.1.1	Study Treatment Administration Through Day 43	Safety
14.2.1.2	Study Treatment Administration by Additional Treatment Visit	Safety
14.2.2.1	Concomitant Medications Through Day 43	Safety
14.2.2.2	Concomitant Medications For Additional Treatment Visits	Safety
14.2.3.1.1	Change from Baseline in PSA by Visit Through Day 43	Safety
4.2.3.1.2	Change from Baseline in PSA by Additional Treatment Visit	Safety
14.2.3.2.1	Summary of PSA Velocity and PSA Doubling Time Through Day 43	Safety
14.2.3.2.2	Summary of PSA Velocity and PSA Doubling Time Through End of Treatment	Safety
14.2.3.2.3	Summary of PSA Velocity and PSA Doubling Time Through End of Study	Safety
14.3.1.1.1	Summary of Worst Administration Site Reactions Through Day 43 by Grade	Safety
14.3.1.1.2	Summary of Worst Administration Site Reactions For Additional Treatment Visits by Grade	Safety
14.3.1.2.1	Summary of Administration Site Reactions by Visit Through Day 43 and Grade	Safety
14.3.1.2.2	Summary of Administration Site Reactions by Additional Treatment Visit and Grade	Safety
14.3.2.1.1	Overall Summary of Adverse Events Through Day 43	Safety
14.3.2.1.2	Overall Summary of Adverse Events For Additional Treatment Visits	Safety
14.3.2.2.1	Treatment-Emergent Adverse Events (TEAE) by System Organ Class and Preferred Term Through Day 43	Safety
14.3.2.2.2	Treatment-Emergent Adverse Events (TEAE) by System Organ Class and Preferred Term For Additional Treatment Visits	Safety
14.3.2.3.1	Treatment-Emergent Adverse Events (TEAE) by System Organ Class and Severity Through Day 43	Safety
14.3.2.3.2	Treatment-Emergent Adverse Events (TEAE) by System Organ Class and Severity For Additional Treatment Visits	Safety
14.3.2.4.1	Treatment-Emergent Adverse Events (TEAE) by Preferred Term and Relationship to Study Treatment Through Day 43	Safety
4.3.2.4.2	Treatment-Emergent Adverse Events (TEAE) by Preferred Term and Relationship to Study Treatment For Additional Treatment Visits	Safety
4.3.2.5.1	Serious Treatment-Emergent Adverse Events (TEAE) by System Organ Class and Preferred Term Through Day 43	Safety
4.3.2.5.2	Serious Treatment-Emergent Adverse Events (TEAE) by System Organ Class and Preferred Term For Additional Treatment Visits	Safety

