14.3.2.6.1	Treatment-Emergent Adverse Events (TEAE) Leading to Permanent Dose Discontinuation by System Organ Class and Preferred Term Through Day 43	Safety

14.3.2.6.2	Treatment-Emergent Adverse Events (TEAE) Leading to Permanent Dose Discontinuation by System Organ Class and Preferred Term For Additional Treatment Visits	Safety
14.3.2.7	Listing of Serious Treatment Emergent Adverse Events	Safety
14.3.3.1.1	Change from Baseline in Hematology Parameters by Visit Through Day 43	Safety
14.3.3.1.2	Change from Baseline in Hematology Parameters by Additional Treatment Visit	Safety
14.3.3.2.1	Change from Baseline in Chemistry Parameters by Visit Through Day 43	Safety
14.3.3.2.2	Change from Baseline in Chemistry Parameters by Additional Treatment Visit	Safety
14.3.3.3.1	Change from Baseline in Coagulation and CH50 Parameters by Visit Through Day 43	Safety
14.3.3.3.2	Change from Baseline in Coagulation and CH50 Parameters by Additional Treatment Visit	Safety
14.3.4.1	Change from Baseline in Vital Sign Parameters by Visit Through Day 43	Safety
14.3.4.2	Change from Baseline in Vital Sign Parameters by Additional Treatment Visit	Safety
14.3.5.1.1	ECOG Performance Score by Visit Through Day 43	Safety
14.3.5.1.2	ECOG Performance Score by Additional Treatment Visit	Safety
14.3.5.2	Shift from Baseline in ECOG Performance Score (Worst Case) Through Day 43	Safety
14.3.6.1.1	Change from Baseline in ECG Parameters by Visit Through Day 43	Safety
14.3.6.1.2	Change from Baseline in ECG Parameters by Additional Treatment Visit	Safety
14.3.6.2	Shift from Baseline in ECG Overall Interpretation by Visit	Safety
14.4.1.1	Summary of Antigen-Specific anti-HAAH Antibody Titers by Visit Through Day 43	Immmunologic
14.4.1.2	Summary of Antigen-Specific anti-HAAH Antibody Titers by Additional Treatment Visit	Immmunologic
14.4.2.1	Summary of Cellular Immune Response by Visit Through Day 43	Immmunologic
14.4.2.2	Summary of Cellular Immune Response by Additional Treatment Visit	Immmunologic
14.4.3.1	Summary of Immunophenotyping by Visit Through Day 43	Immmunologic
14.4.3.2	Summary of Immunophenotyping by Additional Treatment Visit	Immmunologic

Figure No.	Description of Figure	Population
14.4.1.1	Mean (SD) of H460 (HAAH) by Treatment	Immmunologic
14.4.1.2	Mean (SD) of HAAH-1 λ by Treatment	Immmunologic
14.4.2.1	Mean (SD) of CD4+ T Cells IFN-γ by Treatment	Immmunologic
14.4.2.2	Mean (SD) of CD8+ T Cells IFN-γ by Treatment	Immmunologic

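### Read literally, SAP 7.4.6 keeps a doubly recorded site reaction that is serious or ends treatment out of counts that SAP 8.6.2 says are complete

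*SAP*

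**What the plan says.** SAP 7.4.6 covers administration site reactions (ASRs) that appear in two places. It concerns an ASR from the AE log which is "also captured on the Physician Administration Site Assessment eCRF page will not be counted as an (unsolicited) AE to avoid duplication". Nothing in the section exempts serious reactions or reactions that end treatment. The word *unsolicited* is not defined and is not used elsewhere in the SAP.

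SAP 7.4.5 says that TEAEs "include all AEs that start on or after the first study treatment administration", with no carve-out for ASRs.

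SAP 8.6.2 then states: "Summaries will be generated for all serious TEAEs and all TEAEs causing permanent dose discontinuation", by system organ class, preferred term and dosage group. The matching entries in SAP 10.1 include "Serious Treatment-Emergent Adverse Events (TEAE) by System Organ Class and Preferred Term Through Day 43" (14.3.2.5.1) and "Treatment-Emergent Adverse Events (TEAE) Leading to Permanent Dose Discontinuation by System Organ Class and Preferred Term Through Day 43" (14.3.2.6.1). Each has a companion table for additional treatment visits.

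For reactions taken from the physician page, SAP 8.6.1 says that the number of subjects with at least one reaction "will be tabulated by reaction type, maximum severity, and dosage group through Day 43", and separately for visits after Day 43.

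On listings, SAP 7.4 says "All collected data will be presented in listings", and SAP 8.6.2 adds "A listing will be produced for all subjects who reported serious TEAEs".

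**The concern.** The exclusion is sensible for general incidence tables, where the same redness or swelling would otherwise appear under both ASRs and AEs. It does not suit the serious and discontinuation tables. Those tables report two attributes that the ASR tables do not carry, so counting the reaction there duplicates nothing.

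For a serious or treatment-ending ASR on both pages, a programmer cannot follow 7.4.6 to the letter and also deliver the complete summaries promised in 8.6.2. If 7.4.6 is followed, the discontinuation table can show no event while the disposition table shows a patient stopping because of one. The serious table can likewise omit a reaction that the serious-event listing displays. In a first-in-human vaccine study where ASR incidence is a named secondary endpoint, those are cells a safety reader looks at first.

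**Working it through.** The plan states no figure on this point, so there is none to reproduce. The check traces one event through the rules and then does simple division.

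**Step 1. Trace the event.** Take an ASR that starts after the first dose, is in the AE log and on the physician page, and is serious or ends dosing.

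| Rule | Result |
|---|---|
| SAP 7.4.5, TEAE definition | It is a TEAE |
| SAP 8.6.2, serious and discontinuation summaries | It must be counted |
| SAP 7.4.6, double recording | It is not counted as an AE |

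The second and third rows cannot both be met. An ASR in the AE log alone does not trigger 7.4.6 and is still counted.

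**Step 2. See what other outputs hold.**

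| Output | What it shows for this event |
|---|---|
| ASR tables 14.3.1.x (SAP 8.6.1) | Type, severity on a 0 to 4 scale, dosage group; not seriousness or discontinuation |
| Disposition (SAP 8.1) | Reason for stopping by dosage group; not the event by class and term |
| By-subject AE listing (SAP 8.6.2) and 14.3.2.7 | The individual event, but no count |

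14.3.2.7 is a listing and 7.4.6 speaks only of counting, so on the plain words the event stays there.

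**Step 3. Count the tables exposed.** The TEAE count tables are 14.3.2.1 to 14.3.2.6, two each: 6 × 2 = 12.
- Directly exposed: 14.3.2.5.x (2) + 14.3.2.6.x (2) = 4.
- Possibly exposed: 14.3.2.1.x (2), if these overall summaries have rows for serious or discontinuation events. SAP 10.1 gives only their titles, and the shells are in a separate document (SAP 10.2).
- Not at issue: 14.3.2.2.x to 14.3.2.4.x = 6 general incidence tables.

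Each pair splits at Day 43, so one event falls in one table of a pair. It can be missing from at most 1 + 1 + 1 = 3 tables, and only in particular cells.

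**Step 4. Size of one missed event.** SAP 7.1 gives cohorts of 3 or 6.
- 1/3 = 33.3%, shown as 0/3 = 0%.
- 1/6 = 16.7%, shown as 0/6 = 0%.

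The top dose cohort is planned at 6 or more evaluable patients (protocol 5.3.5), so 1/3 does not apply to it once filled. These figures assume that the patient has no other TEAE qualifying for the same cell and that the denominator is the whole cohort. After Day 43 patients may change dose level, and denominators may differ.

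**Step 5. How likely is it?** Protocol 5.2.4 provides for withdrawal after a grade 3 ASR, so the route exists. Double recording is less certain. Under protocol Table 1 a nine-dose patient has 4 site checks to Day 43 (Days 1, 8, 22, 43) plus 6 at additional dosing visits = 10, and only Day 8 is not a dosing day. (The synopsis also lists an end-of-study check, which Table 1 does not mark.) A delayed reaction after a later dose may therefore reach the AE log alone. The documents give no rate for either condition.

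**The case against.** The best reply is that this is an ambiguity and not a planned omission. The stated aim of 7.4.6 is to avoid duplication, 8.6.2 is the more specific rule, and *unsolicited* may have been meant to limit the exclusion. The separate shells and programming notes may settle it. This stands in part: the authors may well have intended the narrower rule. But the SAP defines no unsolicited-AE table, no title in 10.1 uses the word, and the 8.6.2 tables are the only AE counts on which 7.4.6 can act. The SAP text should not depend on a document outside it.

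A second reply is that a reader can reconcile the outputs, because grade 3 reactions appear in 14.3.1.x, stopping reasons appear in disposition, and there are only about 18 patients. That is fair as to lost information: none is lost. It does not supply the count that 8.6.2 promises, nor does severity stand in for seriousness. A treatment-ending reaction also need not be grade 3, since protocol 5.2.3 and 5.3.5.2 give other toxicity grounds for stopping.

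A third reply is that the event may never happen. Protocol 3.2 reports no local reactogenicity in mice and rats, and injection-site microscopic findings in the rat toxicology study were judged non-adverse. This stands. Protocol 5.2.4 is a contingency rule, and a reader who infers from it that such withdrawals are expected goes beyond the documents.

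**Conclusion.** The conflict between SAP 7.4.6 and 8.6.2 is real on the text but narrow. It arises only for an ASR that is recorded on both pages and is serious or ends treatment. If that occurs, 7.4.6 is applied literally and the patient has no other qualifying TEAE, a cell reads 0 instead of 1/3 (33.3%) or 1/6 (16.7%). The exposure of 14.3.2.1.x is an inference from its title.

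Three stronger readings are not supported. Serious reactions are not hidden: the listings, the ASR severity tables and the disposition reasons keep them. Dose decisions are not affected: SAP 6.3 places MTD and DLT determination outside the SAP, and SAE reporting follows the protocol. Nor are whole tables wrong, since only the cells for such an event would be. No patient is known to be affected. Low priority.

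**What to change.** Amend SAP 7.4.6 in three respects:
- Limit the exclusion to the general TEAE incidence tables, 14.3.2.2.x to 14.3.2.4.x, and the general rows of 14.3.2.1.x.
- State that serious TEAEs and TEAEs causing permanent dose discontinuation are counted in 14.3.2.5.x, 14.3.2.6.x and any corresponding rows of 14.3.2.1.x, and are kept in 14.3.2.7, whichever page recorded them.
- Footnote the general tables to say that ASRs captured on the physician page are summarised in 14.3.1.x.

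The cost is a short addition and one footnote. No new data are needed, because 14.3.2.5.x and 14.3.2.6.x already require the seriousness and discontinuation fields. The downside is that the serious and discontinuation tables may show a term absent from the general tables; the footnote explains why. Merely footnoting the serious and discontinuation tables would disclose the exclusion but leave the commitment in 8.6.2 unmet.
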